4. SELECTION AND WITHDRAWAL OF SUBJECTS

Male and female subjects, 18 years of age or older, with a clinical diagnosis of AA, AU or AT of the scalp, who meet all the inclusion criteria and none of the exclusion criteria, will be eligible to enroll in this study.

4.1. Subject Inclusion Criteria

Protocol: ATI-502-AA-203

Subjects must meet the following criteria to be eligible for participation in the study:

- 1. Subject must be able to comprehend and willing to sign the Informed Consent Form (ICF).
- 2. Male or non-pregnant, non-nursing female ≥ 18 years old at the time of informed consent.
- 3. Subject has completed 24 weeks of treatment in study ATI-501-AUAT-201.
- 4. Subject has not experienced any clinically significant AEs, SAEs or tolerability issues that met study discontinuation criteria in ATI-501-AUAT-201.
- 5. Subject is capable of regrowing scalp hair or maintaining prior scalp hair regrowth from ATI-501-AUAT-201 in the opinion of the investigator.
- 6. If a woman of childbearing potential (WOCBP), must have a negative urine pregnancy test at Visit 1 and agree to: use a highly effective method of birth control for the duration of the study; not be planning a pregnancy during the study duration and use contraception for 30 days after last application of study medication. (Refer to Section 8.4).
- 7. Be in good general health and free of any known disease state or physical condition which, in the investigator's opinion, might impair evaluation of the subject or which might expose the subject to an unacceptable risk by study participation.
- 8. Be willing to maintain the same hair style throughout the study period. Subjects who shave their scalp must be willing to refrain from shaving their scalp for at least one week or longer prior to each study visit, as determined by the investigator based on visible scalp hair growth. Hair trimming outside the treatment areas to maintain the current hair style is permitted.
- 9. Be willing and able to follow all study instructions and to attend all study visits.
- 10. Sexually active male subjects must agree to use a barrier method of contraception from the first application of study medication to at least 30 days after the last application of study medication.

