ALODEX Score (after SALT) ¹¹	✓	(X) [^]		X	X	X	X	X
Vellus and Indeterminate Hair Assessment	✓	(X) [^]		X	X	X	X	X
Photography (complete scalp)	✓	(X) [^]		X	X	X	X	
Subject instructions ¹²		X	X	X	X	X		
In office study medication application		X						
Dispense study medication ¹³		X	X	X	X	X		
Collect study medication and assess compliance ¹⁴			X	X	X	X	X	
Concomitant therapies	√	(X) [^]	X	X	X	X	X	X
Adverse events	√	(X) [^]	X	X	X	X	X	X

Abbreviations: CR= Clinician Rating; ET= Early termination Visit; SR= Subject Rating

¹Visit 1 will occur on the same day as Visit 9 of study ATI-501-AUAT-201. Visit 9 procedures for study ATI-501-AUAT-201 must be completed prior to initiation of any study related activity for ATI-502-AA-203. Eligible subjects must sign consent prior to first application of topical study medication. The assessments performed for Visit 9 in study ATI-501-AUAT-201 will be entered into the source document and eCRF for Visit 1 in study ATI-502-AA-203. ATI-502-AA-203 enrollment may not be open at the time of a subject's ATI-501-AUAT-201 Visit 9. If this scenario occurs, the subject may be brought back to the clinic prior to their ATI-501-AUAT-201 Visit 10. At this visit, the subject will then be given topical treatment. Assessments marked as (X)^ represent repeat assessments that would need to be performed if the subject cannot enroll directly at Visit 9 (or within 14 calendar days of Visit 9) from study ATI-501-AUAT-201.

²A written, signed ICF must be obtained from each subject prior to performing any study related procedure.

³A physical examination includes: General appearance, examination of the head, eyes, ears, nose and throat, respiratory, cardiovascular, abdominal, extremities, musculoskeletal, lymphatic, skin (other than AA) and neurological assessment.

⁴Vital signs include oral or ear temperature, blood pressure, heart rate, respiration rate.

⁵ For WOCBP, the UPT performed at Visit 9 in study ATI-501-AUAT-201 must be negative prior to study medication application. UPT in WOCBP must also be obtained at Visits 3, 4, 5, 6, and 7 and must be negative for the subject to continue in the study.

⁶ The subject should perform assessments prior to the Investigator assessments. The investigator may assist the subject in locating a Target Patch.

⁷The subject should refer to the Baseline (Visit 2 from ATI-501-AUAT-201 and Visit 1 from ATI-502-AA-203) photographs when assessing the change over time.

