8.4.1. Definition of Women of Child Bearing Potential (WOCBP)

WOCBP includes any female who has experienced menarche and who has not undergone successful surgical sterilization (*e.g.*, hysterectomy, bilateral tubal ligation, or bilateral oophorectomy) or is not postmenopausal. Postmenopausal is defined as ≥12 months with no menses without an alternative medical cause. WOCBP must have a negative UPT at Visit 9 (study ATI-501-AUAT-201)/Visit 1 (study ATI-502-AA-203) prior to dispensing study medication.

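### A woman of childbearing potential who enters 1 to 14 days after Visit 9 can receive her first application on a pregnancy test up to 14 days old, and the protocol leaves unclear whether that meets inclusion criterion 6

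*Combined protocol and SAP*

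**What the plan says.** Section 4.1, inclusion criterion 6 (repeated in the Synopsis), states that a woman of childbearing potential "must have a negative urine pregnancy test at Visit 1". Under Section 5.1 the first application is made in the office at Visit 1.

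Table 3 (Section 3.6) marks the Visit 1 urine pregnancy test (UPT) as (X)^. Footnote 1 makes same-day entry the rule, but foresees that "enrollment may not be open at the time" of a subject's Visit 9. In that case "the subject may be brought back to the clinic prior to their ATI-501-AUAT-201 Visit 10" to start topical treatment. The (X)^ items are repeated only "if the subject cannot enroll directly at Visit 9 (or within 14 calendar days of Visit 9"). The same footnote says that Visit 9 assessments "will be entered into the source document and eCRF for Visit 1".

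Footnote 5 sets the condition for dosing: "the UPT performed at Visit 9 in study ATI-501-AUAT-201 must be negative prior to study medication application". It then adds that "UPT in WOCBP must also be obtained at Visits 3, 4, 5, 6, and 7". Section 8.4.1 states: "WOCBP must have a negative UPT at Visit 9 (study ATI-501-AUAT-201)/Visit 1 (study ATI-502-AA-203) prior to dispensing study medication".

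**The concern.** The 14-day allowance applies to all (X)^ items as a block. It treats pregnancy status in the same way as hair scores and questionnaires, and the protocol gives no reason for doing so. A test before the first dose is there to prevent fetal exposure, so its age at the first application is what counts. Read literally, criterion 6 wants a test at Visit 1. The schedule does not ask for one when Visit 1 falls 1 to 14 days after Visit 9.

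Two things are at stake. One is the small chance of dosing a woman with an unsuspected pregnancy that the Visit 9 test did not show. The other is that two sites could apply the same eligibility criterion differently, so that one site would see a protocol deviation where the other sees compliance.

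**Working it through.** No sample size, power or error rate bears on this point. The check sets the rules side by side and counts days.

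**Inputs.** Criterion 6 (Section 4.1); the UPT row and the inclusion/exclusion row of Table 3; footnotes 1 and 5; Sections 8.1.6, 8.4.1 and 8.4.2.

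**Step 1: age of the test at first application.** Let d be the number of days from Visit 9 to Visit 1. With no repeat, age = d. With a repeat at Visit 1, age = 0.

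| Entry | Repeat UPT under Table 3 and footnote 1? | Age of result at first application |
|---|---|---|
| d = 0 | not needed | 0 days |
| d = 1 to 14 | not required | 1 to 14 days |
| d = 15 or more | required | 0 days |

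The maximum is 14 days, reached just before the point at which the same table asks for a fresh test.

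**Step 2: which text creates the allowance.** It comes from the (X)^ mark together with footnote 1. Footnote 5 waives nothing. It names the Visit 9 UPT as the test that must be negative, and it lists no further test before Visit 3.

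**Step 3: does other text settle the matter?**
- Section 8.4.1 joins Visit 9 and Visit 1 with a slash. It sets no maximum age for the result and does not say which visit governs when the two fall on different days.
- Section 8.1.6 refers back to Table 3 for timing.
- The inclusion/exclusion row of Table 3 is a plain X at Visit 1, so eligibility is always checked there. It does not say which UPT result is to be used.

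**Step 4: how far contraception covers the gap.** Section 8.4.2 requires at least 30 days of stable use before study entry for implants, injectables, patches and combined oral contraceptives, and at least 30 days since insertion for intrauterine devices. For entry on day d, that period starts at least 30 − d days before Visit 9: 30 − 1 = 29 days for d = 1, and 30 − 14 = 16 days for d = 14. For these methods the whole interval between test and dose is covered. No such period is set for abstinence or a vasectomised partner, which are also accepted.

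**The case against.** The strongest reply is that there is no contradiction. Visit 9 results become the Visit 1 record under footnote 1, and Section 8.4.1 treats the two visits as one time point. On that reading a negative Visit 9 test satisfies criterion 6, and the protocol has a coherent 14-day validity window. Alternatively, if criterion 6 is read literally, it governs: Section 4 requires every inclusion criterion to be met, and footnote 1 does not forbid a test at Visit 1.

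Much of this stands. A reader might infer that the protocol flatly contradicts itself, but the documents show only that both readings are open and that nothing chooses between them. The reply does not remove the practical point, because copying a result into the Visit 1 record does not make it more recent.

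It can also be said that other rules protect these women. Pregnant women are excluded (Section 4.2), highly effective contraception is required, and drug is withheld when pregnancy is suspected (Section 8.4.2). These rules do lower the risk. The last one acts only on suspicion, however, and the protocol asks for a negative test before dosing in addition to contraception.

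Finally, nothing in the documents shows that 14 days is unsafe or that 0 days is the correct limit. That is true. The case for change is that the safeguard can be made current, and criterion 6 made clear, at almost no cost.

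**Conclusion.** The point holds as a minor one. A site that follows the schedule can give the first application on a result 1 to 14 days old, and the text does not say whether that result meets criterion 6. Only women of childbearing potential who enter on days 1 to 14 after Visit 9 are affected. Their number is not given and may be zero. Endpoints, estimates and analysis are unaffected.

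Two stronger readings are not supported.

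- **An unusually long gap between tests.** With Visit 3 on Day 29 ± 3, the interval from the Visit 9 test to the next one could reach 14 + 28 + 3 = 45 days. That is not the longest in the schedule: Visits 4 to 5 (113 − 57) and Visits 5 to 6 (169 − 113) are each 56 days apart. What matters here is the age of the test at first exposure.
- **A number of missed pregnancies.** Section 8.1.6 gives the kit sensitivity (25 mIU/mL) but no time from conception to a positive result, so no such number can be derived. A repeat test would narrow the gap but could not exclude a very recent conception.

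The conclusion assumes that sites apply the (X)^ rule as written and do not test at Visit 1 of their own accord.

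**What to change.** In Table 3 footnote 1, state that the 14-day allowance does not extend to the urine pregnancy test. In footnote 5 and Section 8.4.1, state that the Visit 9 test qualifies only when Visit 1 is on the same day, and that otherwise a negative test is needed on the day of first application, before study medication is dispensed. Criterion 6 can then stay as it is.

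The cost is one urine test, with kits already provided by the central laboratory (Section 8.1.6), for each woman of childbearing potential who enters on days 1 to 14. She is at the clinic that day in any case. Same-day entrants are unaffected, and entrants from day 15 are already tested.

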4.2. Subject Exclusion Criteria

Subjects are excluded from this study if any 1 or more of the following criteria is met:

- 1. Any study medication discontinuation criteria are met during participation in study ATI-501-AUAT-201.
- 2. Females who are nursing, pregnant, or planning to become pregnant for the duration of the study and up to 30 days after the last application of study medication.
- 3. The presence of a permanent or difficult to remove hairpiece or wig that will, in the opinion of the investigator, interfere with study assessments if not removed at each visit.
- 4. Sensitivity to any of the ingredients in the study medications.

Date: 09NOV2018, Version 1.0 Page 29 of 80 CONFIDENTAL

5. Unwillingness to refrain from weaves, hair extensions, or shaving of the scalp for at least one week or longer prior to each study visit, as determined by the investigator based on visible scalp hair growth the duration of the study.

4.3. Subject Withdrawal Criteria

Protocol: ATI-502-AA-203

Subjects will be informed that they are free to withdraw from the study at any time and for any reason. The investigator may remove a subject from the study if, in the investigator's opinion, it is not in the best interest of the subject to continue the study. Examples of other reasons subjects may be discontinued from the study are: a change in compliance with an inclusion or exclusion criterion, occurrence of AEs, occurrence of pregnancy, use of a prohibited therapy or subject is unwilling or refuses to continue with the protocol defined study visits and/or subject withdraws consent (Refer to Section 3.4.1.2 for study medication discontinuation or termination criteria).

In case of premature discontinuation from study participation, all efforts will be made to perform all Week 24 (Visit 6) assessments. The date the subject is withdrawn from the study and the reason for discontinuation must be recorded in the subject's electronic case report forms (eCRFs). All withdrawn subjects with ongoing AEs will be followed until the event has resolved or stabilized, until the subject is referred to the care of a local health care professional, or until a determination of a cause unrelated to the study medication or study procedures is made.

Date: 09NOV2018, Version 1.0 Page 30 of 80

5. TREATMENT OF SUBJECTS

Protocol: ATI-502-AA-203

5.1. Study Medication Administration

Study medication will be applied by the subject. Subjects will be instructed to apply a thin film of ATI-502 Topical Solution up to 4-mLs, twice-daily; once in the morning and approximately 12 hours later to the entire scalp and eyebrows (if applicable) following the instructions in Appendix 13 and Appendix 14 (if applicable). The subject must wash her/his hands thoroughly before and after each study drug application. At each study visit, subjects should bring the study medication including unused bottles back to the site. The disposable droppers and applicators should be disposed of at the subject's home.

Following review of study medication instructions, subjects will apply the first dose of study medication in the office under the instruction and supervision of the study staff. During Visit 1, the study staff member will:

- Dispense the appropriate study medication bottle.
- Weigh the bottle with the cap prior to the first study medication application.
- Instruct the subject on the appropriate application technique following instructions in Appendix 13 and Appendix 14 (if applying study medication to the eyebrow area).
- Observe the subject's first study medication application to ensure proper coverage and monitor the subject for at least 20 minutes after application.
- Record the quantity in mLs of study medication the subject applied to cover the entire scalp in the source document, eCRF and on the subject instruction sheet.
- After the first application, the study staff should weigh the study bottle with the cap.
- Provide feedback on the application procedure, if needed.

The investigational site staff will dispense a sufficient supply of study medication at the visits detailed in the Schedule of Assessments (Table 3) and will review the study medication instructions as detailed in Appendix 13 and Appendix 14. At each study visit, subjects should bring the study medication including used and unused bottles and the completed compliance record. The study staff will review the compliance record, used and unused bottles and the study medication instructions.

5.2. Concomitant Medications

Concomitant therapies are any new or existing therapies received from Visit 1 until discharge from the study. Concomitant therapies include drug (e.g. prescription and over the counter [OTC]), and non-drug (e.g., chiropractic, physical therapy, energy-based treatments).

Subjects will be allowed to take medications not restricted by the protocol as long as they have been reviewed by the investigator and will not affect efficacy or safety. Vitamins, minerals, and dietary supplements are permitted while on study if the subject has been on a stable dose prior to study entry and, in the opinion of the Investigator, will not affect the safety or efficacy of the subject during the study. Topical hair and scalp products (shampoos, conditioners, styling products) should be reviewed by the Investigator and are permitted if, in the Investigator's opinion, they will not affect the safety or efficacy of the subject during the study. Use of hair dyes is permitted during the study if the subject uses the same hair dye throughout the study. If

Date: 09NOV2018, Version 1.0 Page 31 of 80 CONFIDENTAL

in the opinion of the Investigator, the hair dye interferes with study assessments the subject may be directed to wait until after the study visit to dye his or her hair. Efforts should be made to keep the hair care regimen the same throughout the duration of the study.

Topical therapies such as topical corticosteroids are permitted if they are not applied on or near the scalp and if applicable the eyebrow(s) and are not used for hair growth in other areas. Inhaled or intranasal corticosteroids are allowed in the study.

Prior permitted concomitant medications taken within 30 days of beginning treatment with ATI-502 Topical Solution will be documented in the subject's source document and eCRF. In addition, any new permitted medications administered during protocol treatment and through Week 28 (Visit 7?) will be documented in the subject's source document and eCRF.

5.3. Grooming

Protocol: ATI-502-AA-203

Routine shaving of the scalp and beard is allowed during the study if the subject refrains from shaving for a period sufficient to show hair growth prior to Visits 4 and 6. Subjects who shave their scalp must be willing to refrain from shaving their scalp for at least one week or longer prior to each study visit, as determined by the investigator based on visible scalp hair growth. Hair trimming outside the treatment areas to maintain the current hair style is permitted. Subjects are allowed to grow their hair longer than the length at the baseline visit (Visit 1), as long as the investigator can assess hair loss and regrowth during the study and hair regrowth is pinned out of the way to show the areas with hair loss at baseline for photographs.

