3.6. Study Procedures

The investigator, a designated and appropriately trained staff member, or the subject will perform the study assessments according to the Schedule of Assessments (Table 3). The same staff member should perform the assessments for a given subject throughout the study. If this becomes impossible, an appropriate designee with overlapping experience with the subject and study should perform the assessments. The same lighting conditions and subject positioning should be used for all evaluations for a given subject.

Date: 09NOV2018, Version 1.0 Page 25 of 80 CONFIDENTAL

Table 3: Schedule of Assessments

Protocol: ATI-502-AA-203

		Visit 9 ¹ from Study							Post- Treatment
Assessi	ments	ATI-501- AUAT-201	Visit 1 ¹	Visit 2	Visit 3	Visit 4	Visit 5	Visit 6 (ET)	Visit 7
12.12.2.12.12	Week	NA	0	2	4	8	16	24	28
	Treatment Day	NA	1	15	29	57	113	169	197
	Treatment Window(days)	N/A	N/A	± 3	± 3	± 3	± 3	± 3	± 7
	ed consent ²		X						
	on/exclusion criteria		X						ļ
	ıl exam ³	✓	(X) [^]					X	
	raphics and Medical History Update		X						
	ia Areata History (Transcribe)		X		37	77	37	37	77
Vital si		√	(X) [^]		X	X	X	X	X
	l CBC, Chemistry, Urinalysis	·			X	X	X	X	X
	regnancy test ⁵	✓	(X) [^]		X	X	X	X	X
ECG		✓							
	Alopecia Scalp Appearance Assessment (ASAA-AAP: SR or ASAA-AT/AU: SR)	√	(X) [^]			X		X	X
	Alopecia Facial Hair Appearance Assessment (AFHA: SR)	✓	(X) [^]			X		X	X
يو ا	Subject Global Impression of Severity (SGIS-AAP or SGIS-AT/AU)	✓	(X) [^]			X		X	
Subject ⁶	Alopecia Impact Assessment (AIA): Subject Rating	✓	(X) [^]			X		X	
~	Subject Global Impression of Change (SGIC) ⁷	✓						X	
	Subject Global Impression Treatment Satisfaction (SGITS-AAP or SGITS-AT/AU) ⁸	√	(X) [^]			X		X	
	Subject Global Satisfaction with Hair Quality (SGSHQ-AAP or SGSHQ-AT/AU)	✓	(X) [^]			X		X	
	Alopecia Scalp Appearance Assessment (ASAA: - AAP:CR of ASAA-AT/AU:CR)	✓	(X) [^]			X		X	X
Investigator ⁶	Alopecia Facial Hair Appearance Assessment (AFHA: CR)	✓	(X) [^]			X		X	X
tig	Non-Scalp Hair Loss Assessment (NSHA)	✓	(X) [^]			X		X	
Inves	Physician Global Impression of Severity (PhGIS-AAP or PHGIS-AT/AU)	✓	(X) [^]			X		X	
1	Physician Global Impression of Change (PhGIC)	✓	(X) [^]					X	
	Hair Quality Assessment (Patchy AA Subjects Only) ⁹	✓	(X) [^]			X		X	X

Assessments	Visit 9 ¹ from Study ATI-501- AUAT-201	Visit 1 ¹	Visit 2	Visit 3	Visit 4	Visit 5	Visit 6 (ET)	Post- Treatment Visit 7
SALT Score (prior to ALODEX) ¹⁰	✓	(X) [^]		X	X	X	X	X

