Date: 09NOV2018, Version 1.0 Page 39 of 80 CONFIDENTAL

A little hair, whole scalp mostly exposed
☐ No hair, whole scalp completely exposed
7.2.2. Alopecia Facial Hair Appearance Assessment (AFHA) for AA, AT and AU: Clinician Rating (CR) (AFHA: CR)
For subjects with AA, AU or AT, the appearance of the subject's facial hair (eyebrows, eyelashes and if male, beard) will be assessed using the AFHA: CR by the investigator at the visits listed in the Schedule of Assessments (Table 3).
The AFHA: CR is the investigator's assessment of the subject's facial hair (eyebrow(s), eyelashed and if male, beard) at a particular point in time. The investigator should NOT refer to any other assessments to assist with these assessments. The investigator or designee will assess the affected facial hair areas (eyebrows, eyelashes and if male, beard) using the scales below and report the one esponse that best describes the amount of eyebrow, eyelash and if applicable beard hair present. Right and left eyebrow and eyelashes should be evaluated separately. The AFHA is a tool to assess the presence of hair in expected areas of growth. As such, unexpected hair growth (e.g. facial/bear hair in women) should be documented as an adverse event rather than on the AFHA.
Instructions for item 1a: Please mark an "X" in the box () that best describes the appearance of the subject's left eyebrow hair right now. Please select the one response that best represents your answer.
Full eyebrow hair
☐ Most eyebrow hair
Some eyebrow hair
A little eyebrow hair
☐ No eyebrow hair
Instructions for item 1b: Please mark an "X" in the box () that best describes the appearance of the subject's right eyebrow hair right now. Please select the one response that best represents your answer.
☐ Full eyebrow hair
☐ Most eyebrow hair
Some eyebrow hair
A little eyebrow hair
☐ No eyebrow hair

Aclaris Therapeutics, Inc.

Date: 09NOV2018, Version 1.0 Page 40 of 80 CONFIDENTAL

Protocol: ATI-502-AA-203

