Instructions for item 2a: Please mark an "X" in the box () that best describes the appearance of the subject's **left** eyelashes right now. Please select the one response that best represents your answer. Full eyelashes Most eyelashes Some eyelashes A little eyelashes No eyelashes **Instructions for item 2b:** Please mark an "X" in the box () that best describes the appearance of the subject's **right** eyelashes right now. Please select the one response that best represents your answer. Full eyelashes Most eyelashes Some eyelashes A little eyelashes ☐ No eyelashes **Instructions for item 3:** Please mark an "X" in the box () that best describes the appearance of the subject's beard hair right now. Beard hair can include hair on the chin, cheeks, neck, and above the upper lip. Please select the one response that best represents your answer. Full beard hair Most beard hair Some beard hair A little beard hair No beard hair

Aclaris Therapeutics, Inc.

Date: 09NOV2018, Version 1.0 Page 41 of 80 CONFIDENTAL

Protocol: ATI-502-AA-203

Aclaris Therapeutics, Inc.

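### Section 5.3 restricts beard shaving only before Visits 4 and 6, but the beard is also rated at Visit 7 and at any repeated Visit 1

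*Combined protocol and SAP*

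**What the plan says.** Section 5.3 (Grooming) has two sentences on shaving. The first covers scalp and beard together and allows shaving if the subject "refrains from shaving for a period sufficient to show hair growth prior to Visits 4 and 6". The second is addressed to people who shave the scalp; they "must be willing to refrain from shaving their scalp for at least one week or longer prior to each study visit". Inclusion criterion 8 in Section 4.1 follows the second sentence: "Subjects who shave their scalp must be willing to refrain from shaving their scalp for at least one week or longer". Exclusion criterion 5 in Section 4.2 likewise concerns only the scalp.

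Table 3 has two rows for facial hair, "Alopecia Facial Hair Appearance Assessment (AFHA: SR") and "Alopecia Facial Hair Appearance Assessment (AFHA: CR"). Both are marked at Visits 4, 6 and 7. Both also carry the repeat mark at Visit 1, which applies when a subject cannot enrol directly at, or within 14 days of, Visit 9 of the previous study.

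The beard is part of this instrument in men. Section 7.2.2 says that "the appearance of the subject's facial hair (eyebrows, eyelashes and if male, beard) will be assessed using the AFHA: CR". The clinician's choices for the beard are "Full beard hair Most beard hair Some beard hair A little beard hair No beard hair". The subject form in Appendix 3 has the same five levels and one further option, for women.

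Change from baseline in AFHA, by visit, is a secondary endpoint (Section 2.2.2). Section 9.4.2 calculates the secondary endpoints against both the current-study baseline and the baseline of the previous study.

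**The concern.** The protocol restricts shaving before two of the AFHA visits because a shaved face cannot be rated for hair growth. The same reasoning applies to the other visits at which the beard is rated, and the rule does not mention them. A by-visit series in which some ratings are protected from shaving and others are not is not comparable across visits.

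Visit 7 is the awkward place for the gap. It is the post-treatment visit, Section 3.1 lists Week 28 among the time points for response and durability, and Section 1.5 describes hair loss soon after oral JAK inhibitors are stopped. A fall in the beard rating caused by shaving would resemble the effect the visit is meant to detect. It could not be checked afterwards from the planned photographs: Table 3 schedules photographs of the scalp and none at Visit 7.

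**Working it through.** There is no planned figure to reproduce. The check compares visit lists and then follows the effect through the rating scale.

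**Step 1: visits.** Inputs are Section 5.3 and Table 3.

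- Post-baseline visits with a beard rating: {4, 6, 7}.
- Visits with a beard-shaving restriction: {4, 6}.
- Not covered: {7}, which is 1 of 3 post-baseline ratings. A repeated Visit 1 is also not covered.
- For the scalp the uncovered set is empty, because the second sentence of Section 5.3 applies at every visit.

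**Step 2: can the form absorb a shaved beard?** Item 3 asks for the appearance at that moment on five levels, with no response for shaved or not assessable (Section 7.2.2, Appendix 3). Section 7.2.2 also tells the investigator not to consult other assessments when rating.

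**Step 3: direction.** Number the levels k = 1 (none) to 5 (full). Take a man whose true beard stays at level k throughout, and assume the worst case, that a shaved beard is rated 1. A shaved rating is then k − 1 levels too low. With Visits 4 and 6 unshaven, as the protocol requires:

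| Baseline | Visit 7 | Apparent change from baseline, Visits 4 and 6 | Apparent change from baseline, Visit 7 | Visit 6 to Visit 7 |
|---|---|---|---|---|
| Unshaven | Shaved | 0 | −(k − 1) | −(k − 1) |
| Shaved | Shaved | +(k − 1) | 0 | −(k − 1) |
| Shaved | Unshaven | +(k − 1) | +(k − 1) | 0 |

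False loss from baseline at Visit 7 therefore needs an unshaven baseline. False loss from Visit 6 to Visit 7 needs only a shaved Visit 7. A shaved baseline gives false gain at Visits 4 and 6.

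**Step 4: size.** For one man, k − 1 is 4 from full, 3 from most, 2 from some, 1 from a little and 0 from none. If a fraction f of men are shaved at Visit 7 and their average true level is m, the mean false drop among men is f × (m − 1). With f between 0 and 1 and m between 1 and 5, this runs from 0 to 4. The documents give neither f nor m, nor the share of men among the approximately 80 subjects, so they do not narrow that range.

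**The case against.** The strongest reply is that misrating is possible but not shown. Section 7 says detailed instructions for both sets of assessments will be sent to sites; these are not in the documents and may deal with shaved beards. Section 7.1.2 has staff instruct the subject before each AFHA rating, and the subject knows whether he shaved. Section 3.6 asks for the same assessor throughout, so the Visit 7 rater will usually have seen the man unshaven at Visit 6. A rater may also see stubble. This stands as far as it goes: a shaved man can be rated too low, and nothing in the documents says he will be.

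A second reply is that the endpoint is change from baseline, not change from Visit 6. The usual baseline rating comes from Visit 9 of the previous study, or from that study's own baseline, and its shaving rules are not provided. This also stands. A reader might infer that shaving at Visit 7 always reads as loss from baseline, but the second row of the table shows otherwise.

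A reader might also infer a four-category false loss for any man who shaves. The documents do not support that: four is the limit of the scale and is reached only from a full beard. Nor does the gap reach the scalp, although the first sentence of Section 5.3 names only two visits for it; the second sentence covers the scalp at every visit.

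Finally, the beard is not a treated site (Section 5.1 directs application to the scalp and, if applicable, the eyebrows), and the synopsis plans no inferential analyses. Both limit the importance of the point. Neither removes the mismatch, because no other section sets a beard rule for Visit 7 or a repeated Visit 1.

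**Conclusion.** The point holds as a mismatch between Section 5.3 and Table 3. Followed exactly, the protocol allows the beard to be rated shaved at Visit 7 and at a repeated Visit 1, on forms that cannot record this, while requiring it unshaven at Visits 4 and 6. Week 28 beard ratings can therefore be too low relative to Visit 6, or relative to an unshaven baseline, and a shaved repeated Visit 1 can produce false gain at Visits 4 and 6.

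The conclusion about visits rests on the text alone. The conclusion about bias assumes that some men shave before the uncovered visits and that raters score what they see. The number of men affected and the average shift cannot be derived from the documents.

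The importance is low: one item, in men only, of one descriptive secondary endpoint. SALT, and the durability endpoint built on it, are unaffected. The change is worth making because it is nearly free.

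**What to change.** In Section 5.3, give the beard its own sentence. It should require men to leave the beard unshaven, for long enough to show growth, before every visit at which AFHA is scheduled: Visit 1 if repeated, and Visits 4, 6 and 7. Remove the scalp from that sentence and leave it to the existing one ("refrain from shaving their scalp for at least one week or longer prior to each study visit"), so that the section does not carry two different visit lists for the scalp.

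The cost is wording only, plus a short period without beard shaving before one or two more visits. No visit, procedure or analysis is added.

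The change does not reach ratings already made at Visit 9 under the previous study's rules. Where those are used as baseline, the report should say whether that protocol restricted beard shaving.
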